### **Aim of the study**

To validate in a real life study a self diagnostic assay for SARS-CoV-2 with the advantages of high speed, simple operation and low cost, and overcomes the shortcomings of the existing molecular detection methods. Clinical specimens from patients who were suspected of being infected with 2019-nCoV will be used to evaluate the performance of the assay. In parallel, we will also use molecular assays for the detection of the presence of the viral RNA from nasopharyngeal swabs since PCR is currently the gold standard.

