#### Primary endpoints

- 1) To estimate the rate of SARS-CoV-2 positive cancer patients (undergoing chemotherapy, immunotherapy, biological therapy, radiotherapy or experimental treatments or major surgery) and health professionals in a comprehensive cancer center or in a cancer setting. Patients positive are serially tested with SARS-CoV-2 IgM / IgG Rapid Test to evaluate the immune response in IgG negative patients and the reliability of the test in those patients who develop clinical signs of SARS-CoV-2 during the trial.
- 2) To validate the accuracy of self diagnostic assay by confirmation of IgM and/or IgG positive test with the current gold standard RT-PCR for positive nucleic acid detection of new coronavirus from nasopharyngeal swabs.
- 3) To perform on plasma samples multiplex immunoassay protein quantitation related to markers of inflammation and immunity (IL-6, TNF, INF $\gamma$ , IL1, IL-2). 2.5 ml of plasma will be needed.

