### **Study Population**

Patients or health professionals already tested positive for the viral RNA from nasopharyngeal swabs by RT-PCR. Patients or health professional who are suspected of being infected with SARS-CoV-2 in the hospital. Patients who are considered at high risk for infection and eligible for active therapy and major surgery.

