#### **2. Confirmed cases**

Patients or subjects with positive RT-PCR for SARS-CoV-2. On the basis of meeting the criteria for suspected cases, sputum, throat swabs, lower respiratory tract secretions, and other specimens were tested by real-time RT-PCR for positive nucleic acid detection of new coronavirus; or viral gene sequencing was highly homologous with known new coronaviruses. Patients positive are serially tested with SARS-CoV-2 IgM / IgG Rapid Test to evaluate the immune response in IgG negative patients and the reliability of the test in those patients who develop clinical signs of SARS-CoV-2 during the trial.

3. Patients who are considered at high risk for infection and eligible for active therapy and major surgery

- Frailty (age and multiple comorbidities) planned to receive a standard systemic anticancer treatment comprising chemotherapy and/or immunotherapy and/or radiation therapy or to receive an experimental treatment
- Major surgery or surgery after neoadjuvant chemotherapy and or chemo/radiotherapy

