## Clinical considerations

All patients with epidemiologic history and/or clinical manifestations suspected for COVID will be proposed, according to the clinical judgement, for RT-PCR test for positive nucleic acid detection, irrespective of serological evidence.

All patients tested as IgM positive will have a confirmatory real-time RT-PCR test for positive nucleic acid detection of new coronavirus on sputum, throat swabs, lower respiratory tract secretions, and other specimens.

The 2019-nCov IgG/IgM Rapid Test Cassette (Whole Blood/Serum/Plasma) will be repeated in patients IgM positive for confirming the subsequent IgG positivity.

The tests will be performed locally in each hospital laboratory.

The ASST of Cremona laboratory could perform:

- [name], UO Laboratorio Analisi – ASST di Cremona: SARS-CoV-2 IgG/IgM Rapid Test Cassette (Whole Blood/Serum/Plasma) also for other sites. 1 ml of plasma will be needed;
- [name] SMeL849 – ASST di Cremona: *multiplex* immunoassay protein quantitation related to markers of inflammation and immunity (IL-6, TNF, INF $\gamma$ , IL1, IL-2, ect). 2.5 ml of plasma will be needed.

The lab responsible person in Milano IEO is:

Dr.ssa [name]  
Divisione di Medicina di Laboratorio  
Istituto Europeo di Oncologia

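### The RT-PCR reference specimen for the primary accuracy endpoint is inconsistent and can depend on the IgM result, which would bias sensitivity and specificity in a direction the documents do not settle

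*Combined protocol and SAP*

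**What the plan says.** Three places name the nasopharyngeal swab:

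- Aim of the study describes parallel molecular testing for "detection of the presence of the viral RNA from nasopharyngeal swabs since PCR is currently the gold standard".
- Primary endpoints, item 2, validates the cassette by "confirmation of IgM and/or IgG positive test" against the "current gold standard RT-PCR for positive nucleic acid detection of new coronavirus from nasopharyngeal swabs".
- Study Population describes one group as "Patients or health professionals already tested positive for the viral RNA from nasopharyngeal swabs by RT-PCR".

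Two places give a different list, in which the nasopharyngeal swab is not named:

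- Inclusion Criteria, 2. Confirmed cases: "sputum, throat swabs, lower respiratory tract secretions, and other specimens were tested by real-time RT-PCR".
- Clinical considerations: every IgM-positive patient has a confirmatory RT-PCR "on sputum, throat swabs, lower respiratory tract secretions, and other specimens".

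Clinical considerations also proposes RT-PCR for suspected patients, by clinical judgement and whatever the antibody result, but names no specimen for them. It gives no specimen rule for participants positive on IgG alone, although endpoint 2 includes them.

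The Statistical Plan makes sensitivity and specificity the primary measure of accuracy. It does not identify the specimen that defines the reference and has no rule for combining several results from one person.

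**The concern.** Sensitivity and specificity are interpretable only if the reference classifies people in the same way whatever the index test shows. Here the one rule that assigns a specimen list after enrolment is triggered by the index test itself, through the IgM line. The only specimen named for general parallel testing is the nasopharyngeal swab. A site that follows both statements could verify IgM-positives with one reference and IgM-negatives with another.

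If the two references detect different fractions of infected people, infected participants move between cells of the two-by-two table at different rates in the IgM-positive and IgM-negative rows. Both primary accuracy measures then shift for reasons unrelated to the cassette. Testing is done in each hospital's own laboratory, so sites could also resolve the conflict differently.

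**Working it through.** **Input check.** Performance study, Table 2 (IgM against PCR) reproduces: sensitivity 17/20 = 85.0% (exact 95% CI 62.1 to 96.8) and specificity 48/50 = 96.0% (86.3 to 99.5). These serve below as illustrative true values, Se and Sp.

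**Assumptions, because the documents give no figures.** Infection prevalence p = 20%, with 10% and 40% as a range. RT-PCR specificity is 100%. The reference detects a fraction r1 of infected IgM-positives and r0 of infected IgM-negatives. Everyone has a reference result, and errors are otherwise independent.

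**Expected cells**

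- TP = p × Se × r1
- FN = p × (1 − Se) × r0
- FP = p × Se × (1 − r1) + (1 − p) × (1 − Sp)
- TN = p × (1 − Se) × (1 − r0) + (1 − p) × Sp

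Apparent sensitivity is TP/(TP + FN) and apparent specificity is TN/(TN + FP).

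**Per 1000 participants at p = 20%** (170 infected IgM-positive, 30 infected IgM-negative, 32 uninfected IgM-positive, 768 uninfected IgM-negative)

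| Reference yield r1 / r0 | TP | FN | FP | TN | Sensitivity | Specificity |
|---|---|---|---|---|---|---|
| 70% / 70% (uniform) | 119 | 21 | 83 | 777 | 85.0% | 90.3% |
| 80% / 70% | 136 | 21 | 66 | 777 | 86.6% | 92.2% |
| 90% / 70% | 153 | 21 | 49 | 777 | 87.9% | 94.1% |
| 50% / 70% | 85 | 21 | 117 | 777 | 80.2% | 86.9% |
| 90% / 90% (uniform) | 153 | 27 | 49 | 771 | 85.0% | 94.0% |

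For the 90% / 70% row: TP = 170 × 0.9 = 153, FN = 30 × 0.7 = 21, FP = 170 × 0.1 + 32 = 49, TN = 30 × 0.3 + 768 = 777. Hence 153/174 = 87.9% and 777/826 = 94.1%.

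**Prevalence.** It cancels from apparent sensitivity, so the sensitivity column holds at any p. Apparent specificity does depend on it:

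| r1 / r0 | p = 10% | p = 20% | p = 40% |
|---|---|---|---|
| 70% / 70% | 93.4% | 90.3% | 82.5% |
| 90% / 70% | 95.1% | 94.1% | 91.1% |
| 50% / 70% | 91.7% | 86.9% | 75.4% |

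**Direction.** With r0 fixed, raising r1 increases TP and lowers FP by the same number, leaving FN and TN unchanged. Both measures therefore rise relative to a uniform r0 reference when r1 > r0, and both fall when r1 < r0. Two readings of the plan lead to different cases:

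- The listed specimens are added to the swab and any positive counts. Given the same swab yield in both groups, r1 cannot be below r0, so the measures rise or stay the same.
- The listed specimens replace the swab. Then r1 may lie on either side of r0; if they detect less, both measures fall.

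**The case against.** A reader might infer that the plan gives cassette-positives a more thorough reference than cassette-negatives, and so overstates accuracy. The case against that inference is strong.

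- No section says cassette-negatives have at most a nasopharyngeal swab. For suspected patients tested whatever their serology, no specimen is named.
- The confirmed-case criterion uses the same specimen list and ties it to enrolment, not to the cassette.
- Endpoint 2 prescribes the nasopharyngeal swab for the cassette-positives themselves. The rule in Clinical considerations turns on IgM alone, so it does not split participants by overall cassette result.
- That rule speaks of a single confirmatory test, and its list is open-ended. It can be read as a list of acceptable specimens that does not exclude the nasopharyngeal swab. No any-positive rule is stated.
- With no yields in the documents, the sign is unknown. Even in the favourable 90% / 70% case, apparent specificity (94.1%) stays below the assumed true 96%. Overall agreement is (153 + 777)/1000 = 93.0%, against a true 0.2 × 85% + 0.8 × 96% = 93.8%.
- The model gives everyone a reference result, which Clinical considerations does not arrange in operational terms. The percentages illustrate the mechanism and are not estimates for this study.

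These points stand, and they rule out a claim of overstatement. They do not remove the conflict: for IgM-positives, endpoint 2 and Clinical considerations name different specimens, and the Statistical Plan does not choose between them.

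**Conclusion.** The reference specimen is inconsistent on the primary accuracy endpoint, and following the plan as written can make the reference depend on the IgM result. If it does, and the yields differ, sensitivity and specificity are biased. Relative to a uniform 70% reference at 20% infection, the illustration moves them by +2.9 and +3.8 points (90% against 70%) or by −4.8 and −3.4 points (50% against 70%). Those sizes rest on the assumed yields, prevalence and perfect RT-PCR specificity.

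The documents do not support saying that accuracy is overstated, nor that the reference is set by cassette result as a stated design feature. The supportable conclusion is an unresolved definition with a possible bias of undetermined direction. It should be corrected, and the correction does not depend on the sign.

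**What to change.** Reconcile Aim of the study, Primary endpoints, Study Population, the confirmed-case criterion and Clinical considerations on the RT-PCR specimen. Then state in the Statistical Plan:

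1. The reference for endpoint 2 is RT-PCR on a nasopharyngeal swab, as the Aim and endpoint 2 already name it, applied in the primary analysis regardless of the cassette result.
2. Specimen type is recorded for every RT-PCR.
3. Results from other specimens do not reclassify the primary reference. They enter a labelled sensitivity analysis with its combination rule written down in advance.

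This defines what counts in the analysis and does not restrict clinical testing.

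The direct cost is protocol wording and one data field. Estimates may be slightly less favourable: in the illustration, a uniform 70% reference gives lower apparent specificity than a uniform 90% one (90.3% against 94.0%). Participants without a nasopharyngeal result drop out of the primary accuracy table, so their number should be reported by cassette result. Any swabs beyond the parallel testing described in the Aim would be a separate cost.

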## Statistical Plan

All data recorded will be summarized in tables, graphs and listings. In general, categorical data will be presented using counts and percentages, whilst continuous variables will be presented using the mean, standard deviation, median, minimum, maximum and number of patients.

In tabulations, denominators for calculation of percentages will be taken as the number of non-missing responses.

Primary end-point, the accuracy of tests, will be sensitivity and specificity and they will be calculated for all tests and compared with the appropriate statistical test.

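### Endpoint 1 does not name the test that defines a positive; if it is RT-PCR, the non-missing denominator drops people who were not swabbed and biases the rate upward, by an amount that depends on the cohort mix.

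*Combined protocol and SAP*

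**What the plan says.** All references are to the combined protocol and SAP.

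- **Primary endpoints, item 1** sets the objective: "To estimate the rate of SARS-CoV-2 positive cancer patients", together with health professionals. No defining test is named.
- **Study Population** brings in three kinds of participant: those suspected of infection; those already positive ("Patients or health professionals already tested positive for the viral RNA from nasopharyngeal swabs by RT-PCR"); and a third group, "Patients who are considered at high risk for infection and eligible for active therapy and major surgery".
- **Clinical considerations** governs who is swabbed. "All patients tested as IgM positive will have a confirmatory real-time RT-PCR test". People with an epidemiological history or clinical signs "will be proposed, according to the clinical judgement, for RT-PCR test", whatever their serology. Nothing there calls for RT-PCR in a high-risk patient who is IgM-negative and unsuspected.
- **Statistical Plan** has one denominator rule for all percentages: "denominators for calculation of percentages will be taken as the number of non-missing responses". It makes no exception for endpoint 1 and has no category for a test that was not done.

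Three places point to RT-PCR as the defining test. Confirmed cases are defined by it (Criteria, item 2), and the sentence on serial cassette testing of positives appears both there and in endpoint 1. The Aim of the study calls PCR the gold standard. The Limitations section says the cassette must not be the only basis for diagnosis.

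**The concern.** A rate is interpretable only if the people in its denominator were not chosen for their likelihood of being in the numerator. Here the swab is given mainly to people with a sign of infection, either a positive IgM line or clinical suspicion. If the endpoint is RT-PCR positivity and the denominator is everyone with an RT-PCR result, the plan estimates positivity among those selected for testing, not among the patients and staff named in the endpoint. The high-risk patients awaiting therapy or surgery are affected most, because they have no swab rule of their own.

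Cases already RT-PCR positive at entry add a separate problem. They are positive by selection and raise a pooled rate whichever denominator is used.

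**Working it through.** **No figure to reproduce.** The documents give no expected rate, precision or sample-size derivation for endpoint 1.

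**Inputs from the documents** (Performance study, Table 2): IgM sensitivity Se = 17/20 = 85.0% (95% CI 62.1% to 96.8%); specificity Sp = 48/50 = 96.0% (86.3% to 99.5%). Exact Clopper-Pearson limits reproduce both intervals.

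**Assumptions**, because the documents give no values: RT-PCR is taken as truth; c, s and h are the shares confirmed at entry, suspected and high-risk; ps and ph are true prevalence in the suspected and high-risk groups; u is swab uptake among the suspected. Suspected people not swabbed at first are swabbed if IgM-positive. High-risk people are swabbed only if IgM-positive.

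**Formulas.** Let a(p) = p·Se + (1−p)(1−Sp), the chance of a positive IgM line at prevalence p.

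- Swabbed = c + s[u + (1−u)·a(ps)] + h·a(ph)
- Positives found = c + s·ps[u + (1−u)Se] + h·ph·Se
- True rate = c + s·ps + h·ph
- Reported rate = positives found / swabbed
- Overstatement = reported rate / true rate

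**One case in full.** c = 0, s = 0.2, h = 0.8, ps = 20%, ph = 2%, u = 100%.

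- a(ph) = 0.02×0.85 + 0.98×0.04 = 0.0562
- Swabbed = 0.2 + 0.8×0.0562 = 0.2450
- Positives found = 0.04 + 0.8×0.02×0.85 = 0.0536
- True rate = 0.04 + 0.016 = 5.6%
- Reported over swabbed: 0.0536/0.2450 = 21.9%, or 3.9 times the truth
- Reported over all enrolled: 5.4%, or 0.96 times the truth

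**Overstatement across assumptions**, with no confirmed cases and ps/ph of 10%/1%, 20%/2% and 30%/5%:

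| Suspected share | u = 100% | u = 50% |
|---|---|---|
| 10% | 5.3–6.5 | 6.4–9.0 |
| 20% | 3.6–4.0 | 4.6–6.0 |
| 30% | 2.7–2.9 | 3.6–4.5 |
| 50% | 1.8–1.9 | 2.5–3.0 |
| 70% | 1.4 | 1.9–2.3 |
| 90% | 1.1 | 1.6–1.8 |
| 100% | 1.0 | 1.4–1.7 |

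With confirmed cases and u = 100%, c/s/h of 10/10/80% gives 3.7–4.2, 5/25/70% gives 2.7–3.0, 20/40/40% gives about 1.6, and 10/70/20% gives 1.2.

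**High-risk group alone**, p = 3%, with f the share of IgM-negatives swabbed for any reason:

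Reported rate = [p·Se + f·p(1−Se)] / [a(p) + f(1−a(p))]

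- f = 0: 0.0255/0.0643 = 39.7%
- f = 10%, 25%, 50%: 16.4%, 8.9%, 5.2%

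At f = 0, setting Se and Sp both to their lower limits gives 12.3%, and both to their upper limits 85.7%.

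**All enrolled as denominator.** With no confirmed cases, the ratio to the true rate is 0.85 to 1.00. The floor is Se itself, reached when only IgM-positives are swabbed.

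**The case against.** **Positive may mean the cassette result.** Endpoint 1 names no test, and the definition of a confirmed case is an eligibility definition. If cassette positivity is meant, the design appears to give the cassette to everyone, few results are missing, and this bias largely disappears. A reader might infer that endpoint 1 is an RT-PCR rate; the documents make that likely but never state it. This objection stands, and it makes a definition the first step of the fix.

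**An unswabbed person may not count as missing.** If case status is what is tabulated, someone never swabbed could be counted as not positive and stay in the denominator. The rule does not say so, and with no category for tests not done, the literal reading drops them.

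**High-risk patients can be swabbed.** A reader might infer that the high-risk rate would be no more than the share of IgM-positives that RT-PCR confirms. The documents do not support this: contact or symptoms make any patient a candidate for RT-PCR irrespective of serology, so f = 0 and its 39.7% are an extreme. Endpoint 2 also speaks of confirming a positive IgG line. If either line triggers a swab, Tables 1 and 2 imply sensitivity of 100% and specificity of 94% to 96%. At f = 0 the reported rate would then be 34% to 44% against 3%, so the wider trigger does not remove the bias.

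**The aim mentions wider molecular testing.** "In parallel, we will also use molecular assays for the detection of the presence of the viral RNA from nasopharyngeal swabs" could suggest universal swabbing, which would leave no bias. But it follows a sentence limited to suspected patients, and Clinical considerations sets narrower triggers.

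**The size rests on unstated inputs.** This stands: group mix, prevalence and uptake are all assumed.

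**Conclusion.** The point holds conditionally. If positive means RT-PCR positive, the swab triggers and the non-missing rule together bias the endpoint 1 rate upward. That would be a stated rule producing a wrong number, not only a missing detail. The direction follows because swabbing favours likelier positives; it would vanish under universal swabbing.

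With all suspected people swabbed, the overstatement is 1.0 to 1.9 times when they are at least half the cohort. It is about threefold or more when unsuspected high-risk patients are about 70% or more. With half of the suspected swabbed and a 10% suspected share, it reaches about 9 times. A reader might infer that the trial will report a rate several times too high. The documents do not support that, since they give neither the entry-group shares nor the uptake.

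**What to change.** In the Statistical Plan:

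1. Define positive for endpoint 1, naming the test and specimen.
2. Exempt endpoint 1 from the non-missing rule.
3. Report by entry group. Show cases already RT-PCR positive at entry separately and leave them out of the estimated rate.
4. Use everyone enrolled in each group as the denominator, with RT-PCR not done as its own row.
5. Label RT-PCR positives over all enrolled as a lower bound for that group.
6. Beside it, give a sensitivity range for unswabbed IgM-negatives, using the IgM sensitivity of 85% and its interval of 62.1% to 96.8%. For example, in a high-risk group with 3% true positivity where only IgM-positives are swabbed, the lower bound is 0.03×0.85 = 2.55%. Dividing by 0.968, 0.85 and 0.621 gives 2.6%, 3.0% and 4.1%. The interval comes from only 20 PCR-positive specimens, so state as an assumption that it carries over to each group.
7. Weight by the probability of being swabbed only where some IgM-negatives in that group were swabbed. Where none were, the weights do not exist, and sensitivity observed in the trial would be 100% by construction and correct nothing.

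The cost is SAP wording, an extra table row and a short sensitivity table; no swab rule has to change. The headline rate will be lower and will carry a range.
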